2.2.3 Baricitinib

2.2.3.1 Potential Risks of Baricitinib

Baricitinib is a Janus kinase (JAK) inhibitor indicated for the treatment of adult patients with moderately to severely active rheumatoid arthritis who have had an inadequate response to one or more TNF antagonist therapies.

The US product labeling indicates a boxed warning for the risk of serious infections, malignancies and thrombosis, while warnings and precautions include serious infections, thrombosis, gastrointestinal perforations, abnormal laboratory assessments (potential changes in lymphocytes, neutrophils, hemoglobin, liver enzymes, and lipids), and avoidance with the use of live vaccines.

The Summary of Product Characteristics (SmPC) indicates as special warning and precautions for infections, including TB, hematological abnormalities, viral reactivation, use of live vaccines, increase in blood lipid parameters, increase in hepatic transaminase, malignancy, venous thromboembolism, hypersensitivity, and use of baricitinib with potent immunosuppressive medications.

Baricitinib has an established safety profile with a positive benefit/risk profile in rheumatoid arthritis. An integrated analysis of patients with active RA exposed to baricitinib with 3770 patients and 10,127 patient years for a maximum exposure of 7 years (as of February 2018) was recently published (38). No significant differences were seen for baricitinib 4-mg vs placebo in adverse events leading to permanent drug discontinuation, death, malignancy, serious infection, or major adverse cardiovascular events. Incidence rates for deep vein thrombosis/pulmonary embolism were numerically higher in baricitinib 4-mg vs placebo; Incidence rates were similar by dose in 2-mg/4-mg-extended dataset. Malignancy (excluding non-melanoma skin cancer) Incidence rates were 0.8 (2-mg) and 1.0 (4-mg; as-randomized analysis). Fewer than 1% of patients discontinued due to abnormal laboratory results. The frequency of Herpes zoster was higher for baricitinib 4-mg vs placebo (1.4 vs 0.4) baricitinib 4-mg vs 2-mg (1.4 vs 1.0).

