8.3.5.1 Investigator Reporting of AEs

Information on AEs will be recorded on the appropriate CRF. All clearly related signs, symptoms, and results of diagnostic procedures performed because of an AE should be grouped together and recorded as a single diagnosis. If the AE is a laboratory abnormality that is part of a clinical condition or syndrome, it should be recorded as the syndrome or diagnosis rather than the individual laboratory abnormality. Each AE will also be described in terms of duration (start and stop date), severity, association with the study product, action(s) taken, and outcome.

Any new infection that occurs on study, regardless of infecting agent (i.e., viral or non-viral) will be captured if it is a Grade 3 or 4 AE or SAE. Completion of the Infection Follow-up eCRF page is required for each infection reported as an adverse event or SAE with site of infection and source of culture provided, if available. The purpose is to document the occurrence of new infections by type of infection and not the duration of the new infections. Therefore, capture the first positive result(s) for the new infection (e.g., blood or urine culture, molecular diagnostic test result, etc.); there is no need to capture repeatedly positive results unless there is a new pathogen identified from the same site (e.g., blood) during the infection event. The sponsor will identify infections considered to be opportunistic based on Winthrop et al. 2015.

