Rates of Grade 3 and 4 AE occurrence will be compared between treatment arms using Barnard's exact test and presented. Rates of SAE occurrence will also be compared between treatment arms using Barnard's exact test and presented. Further, the composite endpoint of the occurrence of death, SAE, or Grade 3 or 4 AE described in Section 3.3 will be analyzed as a time to event outcome. A table will present median time to event along with 95% confidence intervals overall for each treatment arm along with the hazard ratio estimate and log rank p-values (Table 73). Differences in time-to-event endpoints by treatment will be summarized with Kaplan-Meier curves.

A summary of the infections reported on the AE CRF will be summarized by treatment group and disease severity (Table 74). The anatomical location(s) of the infection and causative pathogen(s) determined by culture will be summarized. Infections considered to be opportunistic, as identified by the sponsor, will also be included in the summaries.

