N = Number of Subject in the As Treated Population and specified actual disease severity stratum. n = Number of subjects in a given treatment group who experienced the specified safety event outcome. 95% CI calculated using C-P/Blaker method P-value calculated using Barnard's Exact Test							

Table 73: Analysis of Time to Death, SAEs, or Grade 3 or 4 AEs by Treatment Group – As Treated Population

Actual Disease Severity	Treatment Group	n	Median Time		HR		P-value
			Estimate	95% CI	Estimate	95% CI	
Any Severity (N=X)	Baricitinib + RDV (N=X)	X	x.x	x.x, x.x	x.xx	x.xx, x.xx	x.xxx
	Placebo + RDV (N=X)	X	x.x	x.x, x.x			
Moderate (N=X)	Baricitinib + RDV (N=X)	X	x.x	x.x, x.x	x.xx	x.xx, x.xx	--
	Placebo + RDV (N=X)	X	x.x	x.x, x.x			
Severe (N=X)	Baricitinib + RDV (N=X)	X	x.x	x.x, x.x	x.xx	x.xx, x.xx	--
	Placebo + RDV (N=X)	X	x.x	x.x, x.x			

N= Number of subjects in the As Treated Population and specified actual disease severity stratum.

n = Number of subjects who died or experienced SAEs or Grade 3 or 4 AEs.

HR is the ratio of the hazard of Death/SAE/AE of Grade 3 or 4 in each treatment group estimated from the stratified Cox model. The ratio is Baricitinib + RDV to Placebo + RDV. P-value calculated using the Log-rank test

Table 74: Infections by Treatment Group – As Treated Population, Moderate Disease Severity

Anatomical Location	Pathogen	Baricitinib + RDV (N=X)									Placebo + RDV (N=X)								
		Severe			Life-Threatening			Death			Severe			Life-Threatening			Death		
		n	%	Events	n	%	Events	n	%	Events	n	%	Events	n	%	Events	n	%	Events
Any Location	Any Pathogen	x	x	x	x	x	X	x	x	x	x	x	x	x	x	x	x	x	x
Location 1	Any Pathogen	x	x	x	x	x	X	x	x	x	x	x	x	x	x	x	x	x	x
	Pathogen 1	x	x	x	x	x	X	x	x	x	x	x	x	x	x	x	x	x	x
	Pathogen 2	x	x	x	x	x	X	x	x	x	x	x	x	x	x	x	x	x	x
Location 2	Any Pathogen	x	x	x	x	x	X	x	x	x	x	x	x	x	x	x	x	x	x
	Pathogen 1	x	x	x	x	x	X	x	x	x	x	x	x	x	x	x	x	x	x
	Pathogen 2	x	x	x	x	x	X	x	x	x	x	x	x	x	x	x	x	x	x

Note: Percents may not add to 100 because participants may have infections with multiple pathogens. All Grade 3 or 4 infections are also reported as AEs.
 N=Number of participants randomized to Treatment group.
 n=Number of participants with infection.

Tables with similar format:

Table 75: Opportunistic Infections by Treatment Group – As Treated Population, Moderate Disease Severity

Table 76: Infections by Treatment Group – As Treated Population, Severe Disease Severity

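### SAP 9.4 names only culture-determined pathogens for the infection summary although the protocol also collects molecular results, and the Table 74 footnote gives the wrong denominator

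*SAP*

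**What the plan says.** Protocol Appendix B 8.3.5.1 sets what sites collect. A new infection, "regardless of infecting agent (i.e., viral or non-viral) will be captured if it is a Grade 3 or 4 AE or SAE". For each one an Infection Follow-up eCRF page is required, "with site of infection and source of culture provided, if available", and sites are told to "capture the first positive result(s) for the new infection (e.g., blood or urine culture, molecular diagnostic test result, etc". The aim is stated: "The purpose is to document the occurrence of new infections by type of infection and not the duration of the new infections".

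SAP 9.4 sets what is reported. It begins broadly: "A summary of the infections reported on the AE CRF will be summarized by treatment group and disease severity (Table 74". It then narrows the pathogen part: "The anatomical location(s) of the infection and causative pathogen(s) determined by culture will be summarized". Infections that the sponsor classes as opportunistic are added to the summaries.

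The Table 74 shell, whose format Tables 75-79 share, has rows by anatomical location and, within location, an Any Pathogen row followed by generic pathogen rows. Its footnotes include "N=Number of participants randomized to Treatment group". Tables 74-75 are titled for the As Treated population with moderate disease, 76-77 for severe disease, and 78-79 for all subjects.

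**The concern.** The reporting sentence is narrower than the collection rule. The protocol names molecular results alongside culture and covers viral infections explicitly. The SAP gives no rule for an agent identified by PCR, antigen or serology. Two programmers could treat the same PCR-positive infection differently, one giving it a pathogen row and one leaving it out, and both could claim to follow the plan. A pre-specified safety table should not leave that open.

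The agents affected are of interest for this drug. Among the European label cautions that protocol Appendix B 2.2.3.1 lists for baricitinib are "special warning and precautions for infections, including TB, hematological abnormalities, viral reactivation, use of live vaccines". The same section reports herpes zoster at 1.4 on 4 mg versus 0.4 on placebo in rheumatoid arthritis.

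The denominator is a separate slip in the same tables. A stratum-specific count divided by the whole randomized arm gives a percentage that describes no defined group.

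**Working it through.** **Pathogen wording.** This part is a comparison of texts.

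| Item | Protocol App. B 8.3.5.1 | SAP 9.4 text | Tables 74-79 shells, Listing 15 |
|---|---|---|---|
| Infections in scope | New, Grade 3-4 or serious, viral or non-viral | Those on the AE CRF, no limit by test | n is participants with infection |
| How the agent is established | Culture, molecular test, and so on | Culture | Not stated |
| Rule for non-culture agents | Recorded | None | None; generic pathogen rows or columns |

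1. Counting of infections is not restricted. Neither the opening sentence of the SAP paragraph nor the table's definition of n mentions a test method.
2. Naming of pathogens is restricted in the text. The shells are silent, so they neither enforce nor override the culture condition.
3. Other by-arm displays cover this only in part. SAP 9.3 promises adverse event proportions by system organ class and preferred term, but the listed preferred-term shells are limited to events in 5% of subjects (Tables 58-60), renal and hepatic events (61-62) and related events (63). An uncommon viral infection judged unrelated has no by-arm preferred-term shell. Listing 15 is subject-level. Tables 74-79 are therefore the main planned by-arm display of infection type.

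**Denominator.** Tables 72 and 73 define N as As Treated subjects in the specified actual severity stratum, and SAP 6.3 places safety summaries on the As Treated population. The Table 74 footnote departs from both and from its own title.

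Let A be the number randomized to an arm, s the Severe share, and n the number with an infection in the Severe stratum. Ignoring the few untreated subjects:

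- Intended percentage: n / (sA)
- Literal percentage: n / A
- Ratio, literal to intended: s for the Severe tables and, by the same argument, 1 − s for the Moderate tables

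Inputs: A = 1032 / 2 = 516 (protocol Appendix B 9.2, 1:1 allocation). The documents give no value for s. I assume one third.

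- Severe: 516 / 3 = 172 subjects. Each infected subject contributes 1/172 = 0.58% as intended and 1/516 = 0.19% as written; ratio 172/516 = 0.33.
- Moderate: 516 − 172 = 344 subjects. 1/344 = 0.29% against 0.19%; ratio 344/516 = 0.67.
- Any s: the two ratios sum to 1, so at least one stratum's tables show half the intended percentage or less.

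SAP 13 rounds percentages to whole numbers and prints values under 0.5% as <1. Two infected Severe subjects would then print as <1 (2/516 = 0.39%) instead of 1 (2/172 = 1.16%).

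Tables 78-79 pool the strata, so there the literal N differs from the intended one only through untreated or wrongly treated subjects.

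**The case against.** The best defence is that this is loose wording and no data are lost. Much of that stands.

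- The SAP does not say that only cultured agents are shown. The shells and Listing 15 have no culture condition and could carry a PCR result. Exclusion is therefore the literal reading of the text, not an established consequence.
- The protocol's own eCRF sentence mentions the source of culture, which may be where the SAP phrase comes from.
- A reader might infer that even the Any Pathogen row counts cultured organisms only. The definition of n as participants with infection contradicts that.
- A reader might infer that opportunistic infections drop out too. Entry to Tables 75, 77 and 79 depends on the sponsor's classification, not on culture. Only the pathogen rows inside those tables share the ambiguity.
- An infection such as herpes zoster would be recognisable from its adverse event term in the listings whatever the test. The manufacturer's Addendum SAP will specify further safety analyses, which cannot be judged here.
- On the denominator, the table titles already state the population, the counts are printed beside the percentages, and randomization stratified by severity keeps the ratio between arms roughly intact.

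What remains is that the text and the shells do not settle how a molecular result is reported, and that the footnote is wrong as written and shrinks stratum percentages and the differences between them.

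**Conclusion.** Both points hold as specification defects in the infection tables. Read literally, non-culture agents have no pre-specified pathogen line in Tables 74-79, in either arm, while the infections are still counted. The number of infections affected cannot be calculated, because the documents give neither an infection rate nor the share diagnosed without culture. The denominator error, if followed, multiplies each stratum percentage by that stratum's share of the arm: about one third for Severe and two thirds for Moderate under the assumed split.

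It is tempting to conclude that the plan hides an expected excess of viral infection on baricitinib. The documents do not support that. The zoster figures come from rheumatoid arthritis patients with up to 7 years of exposure, and the protocol itself calls extrapolation to COVID-19 difficult, with treatment limited to 14 days. Nor is there a loss of power to report, since Table 74 carries no test or confidence interval. The primary and secondary efficacy analyses are not affected.

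**What to change.** 1. In SAP 9.4, replace the culture condition with: *identified by culture, molecular or other diagnostic test recorded for the infection*. Check that the Infection Follow-up eCRF fields hold non-culture results in the way the protocol asks.
2. In Tables 74-79, define N as As Treated subjects in that arm and, for Tables 74-77, in that actual disease severity stratum, in line with Tables 72-73.
3. Optionally, add a row for infections with no pathogen identified, so that the pathogen rows visibly account for every infection counted.

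The cost is one SAP sentence and one footnote repeated across six tables. The protocol already calls for the data to be collected, and no other analysis changes.

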9.5. Pregnancies

For any subjects in the Treated population who become pregnant during the study, every attempt will be made to follow these subjects to completion of pregnancy to document the outcome, including information regarding any complications with pregnancy and/or delivery. Note that the CSR will not be delayed to wait for outcomes of any pregnancies; an addendum to the CSR would be provided in such a scenario. A set of listings of pregnancies and outcomes will be presented (Listing 14, Listing 15, Listing 16, Listing 17, and Listing 18).

9.6. Clinical Laboratory Evaluations

Clinical safety laboratory adverse events are collected Day 1, 3, 5, 8, 11 and Day 15 and 29 if able to return to clinic or still hospitalized. Parameters evaluated include white blood cell count, absolute neutrophil count, eGFR, platelet count, hemoglobin concentration, creatinine, glucose, total bilirubin, ALT, AST, INR, d-dimer, and CRP. Laboratory safety parameters will be graded according to the Division of AIDS (DAIDS) Table for Grading the Severity of Adult and Pediatric Adverse Events, version 2.1 (July 2017).

The distribution of Grade 3 and 4 chemistry and hematology laboratory results by maximum severity, time point, disease severity and treatment group will be presented ([Table 80](#)).

Treatment-emergent laboratory abnormalities will be summarized by parameter and grade ([Table 83](#)).

Descriptive statistics including mean, median, standard deviation, maximum, and minimum values and change from baseline by time point, for all and each chemistry and hematology laboratory parameter will be summarized by disease severity and treatment arm ([Table 84](#)). Changes in chemistry and hematology laboratory values will be presented in line graphs over time with mean and SD plotted by disease severity and treatment arm ([Figure 53](#)).

Listings will provide a complete listing of individual chemistry and hematology laboratory results with applicable reference ranges ([Listing 19](#)).

9.7. Vital Signs and Physical Evaluations

Vital sign measurements include pulse, systolic blood pressure, respiratory rate, SpO₂ and oral temperature. Vital signs were assessed as part of the NEW score (assessed daily while hospitalized and on Day 15) and will be listed in [Listing 6](#).

Targeted Physical examinations are performed at Day 1 and are performed post-baseline only when needed to evaluate possible adverse events. At the screening visit, the targeted physical examination is focused on lung auscultation. Physical exam findings per subject will be detailed in a listing ([Listing 20](#)).

9.8. Concomitant Medications

Concomitant medications will be coded to the Anatomical Therapeutic Classification using the WHO Drug Dictionary. The use of prior and concomitant medications taken during the study will be recorded on the CRFs. Concomitant medication use will be presented in a subject listing ([Listing 9](#)). The use of concomitant medications during the study (regardless of whether the medications were started prior to enrollment or after enrollment) will be summarized by ATC1, ATC2 code, disease severity and treatment group for the Treated population ([Table 53](#)).

9.9. Other Safety Measures

No additional safety analyses are planned.

10. PHARMACOKINETICS

Not applicable.

11. IMMUNOGENICITY

Not applicable.

12. OTHER ANALYSES

Not applicable.

13. REPORTING CONVENTIONS

P-values ≥ 0.001 and ≤ 0.999 will be reported to 3 decimal places; p-values less than 0.0005 will be reported as “<0.001” and p-values greater than 0.9995 will be reported as “>0.999”.

The mean, standard deviation, median, IQR, and other statistics will be reported to 1 decimal place greater than the original data. The minimum and maximum will use the same number of decimal places as the original data.

Proportions will be presented as 2 decimal places; values greater than zero but <0.005 will be presented as “<0.01”. Percentages will be reported to the nearest whole number; values greater than zero but < 0.5% will be presented as “<1”; values greater than 99.5% but less than 100% will be reported as >99.

Estimated parameters, not on the same scale as raw observations (e.g. hazard ratios and regression coefficients) will be reported to 3 significant figures.

14. TECHNICAL DETAILS

SAS version 9.4 or above, or R language and environment for statistical computing 3.6.1 or above, will be used to generate all tables, figures and listings.

15. SUMMARY OF CHANGES IN THE CONDUCT OF THE STUDY OR PLANNED ANALYSES

The below summarizes the changes made to the SAP from version 2.0 to version 3.0:

In performing the final analyses of the ACTT-1 data, multiple tabular and graphical output required modifications from the shells provided in the ACTT-1 SAP to fix errors, make clarifications, and provide additional supplementary information. After review of the analyses for ACTT-1, multiple ad-hoc analyses were also performed as requested by the sponsor, manufacturer, and FDA. In addition, exploratory analyses of the primary outcome were requested by the ACTT-2 DSMB. The modifications to the ACTT-1 shells as well as the additional analyses requested for ACTT-1 has been added to this version of the ACTT-2 SAP. The additional analyses are all supplemental exploratory analyses and were not driven by review of the ACTT-2 data but were added to provide consistent analyses and summaries across the individual ACTTs.

The additional summaries were added to the TFL appendices of this SAP; general updates were made to the corresponding text within the body of the document, however granular details of each new output were not necessarily added. Note that in adding the additional TFLs, a large number of the existing TFLs were renumbered to conform to eCTD guidelines.

Throughout the document:

- Typos and errors introduced via copying/pasting language from other sections were corrected.
- The Treated Population was renamed as the “As Treated Population”.
- It was clarified that analyses that explore and/or incorporate readmittance will only consider readmittances for COVID-19 reasons.

Section 6.3.1:

- The definitions of the analysis populations were clarified to explicitly denote when the randomized treatment assignment or disease severity stratum would be used versus the actual treatment group or disease severity. TFL shells were updated to explicitly state whether randomized or actual group/severity will be used.

Section 6.4:

- The process for identifying the medications of interest and the categories of medications were updated to match what was used for ACTT-1. Corresponding TFLs were updated accordingly.

Appendices:

- Multiple TFLs were updated to fix omissions/errors and provide additional programming notes.
- The formatting of multiple TFLs was updated to provide better organized and/or more clear displays of the content.

Table 3:

- Included summaries and format was updated to match those used for the corresponding final ACTT-1 table.

Table 4:

- Replaced the term “Completed” with “Received” for infusion summaries throughout.
- Summaries of prior RDV treatment were added.

Table 5 and Table 6:

- Multiple additional protocol deviation tables were added to match those generated for ACTT-1.

Table 16 and Table 17:

- Ad-hoc Fine-Gray, Covariate-Adjusted, and Interaction Modeling analyses of time to recovery were added to match those performed for ACTT-1.

Table 18:

- Restricted Mean Survival Time analysis of time to recovery was added per request by the ACTT-2 DSMB.

Table 19:

- Ad-hoc analysis of time to recovery by prior RDV treatment was added.

Table 35 and Table 36:

- Summaries of clinical status score at individual time points was added to match those generated for ACTT-1.

Table 42, Table 43, Table 44, Table 45, Table 46, Table 47:

- Tables were updated to provide additional summaries which were provided in the ACTT-1 final analyses.

Table 51:

- IQR was added to match the addition to the corresponding table in ACTT-1.

Table 56 and Table 57:

- Additional key safety event categories were added to the table as was requested for ACTT-1. In addition, a table summarizing the risk difference of a subset of these events (difference between treatment groups) was added per request for ACTT-1.

Table 61, Table 62, Table 63:

- Additional summaries of adverse event data were added to match the additions to the ACTT-1 final analyses, including renal AEs, hepatic AEs, and related AEs.

Table 64, Table 65, Table 66, Table 67:

- Disease Severity was added to the tabular summaries.

Table 71:

- Restricted Mean Survival Time analysis of time to death was added per request by the ACTT-2 DSMB.

Table 75, Table 77, Table 79 :

- Opportunistic infection summaries were added; shells were erroneously omitted from previous versions of the SAP.

Table 80, Table 81, Table 82, Table 83:

- A column for Grade 3 or 4 was added as the column was added to the corresponding ACTT-1 table. In addition, disease severity-specific summaries and summaries of treatment-emergent laboratory abnormalities were added, as similar summaries were generated for ACTT-1.

Table 85 and Table 86:

- Disease severity-specific summaries were added.

Figure 6, Figure 7, Figure 8, Figure 9:

- Figures displaying time to recovery Kaplan-Meier curves within subgroups defined by baseline ordinal score were added to match the figures generated for ACTT-1.

Figure 12:

- Forest plot of the hazard ratios of time to recovery by comorbidity was added to match the figure generated for ACTT-1.

Figure 17, Figure 18, Figure 19, Figure 20, Figure 21, Figure 22, Figure 23, Figure 24:

- Figures displaying time to improvement Kaplan-Meier curves within subgroups defined by baseline ordinal score were added to match the figures generated for ACTT-1.

Figure 28, Figure 29, Figure 30, Figure 31:

- Figures displaying time to discharge or NEWS ≤ 2 Kaplan-Meier curves within subgroups defined by baseline ordinal score were added to match the figures generated for ACTT-1.

Figure 44 and Figure 46:

- Figures displaying time to death Kaplan-Meier curves within subgroups defined by disease severity and baseline ordinal score were added to match the figures generated for ACTT-1.

Figure 47, Figure 48, Figure 49, Figure 50:

- Figure displaying time to death Kaplan-Meier curves within subgroups defined by disease severity was added.

The below summarizes the changes made to the SAP from version 1.0 to version 2.0:

Throughout the document:

- Typos and errors introduced via copying/pasting language from other sections were corrected.

Section 3.3.2:

- Language was added to the definition of recovery to note that subjects who are discharged to another hospital, hospice, or similar health care institution will not be considered recovered.

Section 6.4:

- The Prohibited Medications that are being explored in sensitivity analyses were renamed “Medications of Interest”. Corresponding tables and listings were updated accordingly.

Section 6.5:

- Language was added to the imputation rules for clinical scores to note that if a subject terminates early from the study while they are hospitalized or completes the study while still hospitalized without a reported clinical score on the day of discharge, the last observed clinical score assessment will be used as their final assessment.

Section 9.4:

- A supplemental analysis of the time to death outcome was added to explore the interaction between treatment and baseline disease severity with respect to the effect of treatment on the outcome.

Appendices:

- Multiple tables and listings were updated to fix omissions/errors and provide additional programming notes.

